**Aim 2: Compare patient weight loss and diabetes-related outcomes among those who receive obesity screening and counseling to those who do not, following implementation of preventive service coverage.** We will examine post-policy impact of obesity screening and counseling in a cohort of patients with diabetes and at high risk for diabetes. Specific outcomes to be examined include weight loss, diabetes incidence, and diabetes outcomes (including hemoglobin A1c, controlled blood pressure, use of a statin medication). Further, we will determine patient characteristics, including demographics (age, race/ethnicity, rurality), and practice characteristics, including provider type, and their impact on receiving/providing obesity screening and counseling. Understanding patient and practice characteristics most likely to engage in obesity counseling can identify best practices and inform how to increase engagement by both patients and providers.

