Diabetes Service Use	-Clinic visit with primary or secondary diagnosis of diabetes -Emergency department visit with primary or secondary diagnosis of diabetes -Hospitalization with primary or secondary diagnosis of diabetes	Available at all PaTH sites
Exposure variables		
Individual level	-Sociodemographics (e.g., age, sex, race, insurance status, rural vs. urban) -Medical co-morbidities	Available at all PaTH sites
Provider/practice level	-Practitioner type (advanced practice vs. MD/DO) -Practitioner specialty -Practice size (# of providers) -Practice type (multispecialty, academic) -Practice setting (rural vs. urban)	To be determined

**Data Transfer.** The PaTH network has established an operational data infrastructure with the necessary technical safeguards as agreed upon in the PaTH Data Use Agreement (DUA) for sharing and analyzing data while addressing data confidentiality and security concerns. PaTH has deployed two mechanisms for storing, protecting, and sharing data (as described previously under PaTH Governance and Regulatory Issues): (1) data with PHI are stored and protected behind each institution's firewall in the distributed data network and (2) de-identified data are sent to the PaTH data center at

the University of Pittsburgh (CERC-DC). Once data integration is accomplished at each site, sites will remove all PHI and send the de-identified version of the integrated data to the CERC-DC through PaTH's virtual private network/secure file transfer protocol (VPN) which has been operational for data transmission since November 2014. Data analysis can then be performed via secure remote computing using standard statistical software packages (e.g., SAS). This model ensures that the highest level of privacy and confidentiality for the data that are maintained at each site, the CERC-DC, and at Penn State.

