## 8.0 Statistical Plan

Descriptive statistics will be generated to describe the characteristics of different cohorts of interest. The diabetes related outcomes will be summarized at the individual level on a yearly basis. There will be binary outcomes (Yes/No) such as controlled diabetes, controlled blood pressures, receiving annual eye exam, receiving obesity and/or nutritional counseling, and count outcomes such as numbers of clinic visits, emergency department visits and hospitalization, and continuous outcomes such as cost of healthcare utilizations. The distributions of outcome measures will be examined by using minima, maxima, ranges, medians, quartiles, means, and standard deviations for continuous variables, and frequency and contingency tables for categorical variables.

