In the multi-level modeling, the first-level unit is the yearly measurement for the individual subject (pre- and post-policy), the second-level unit is the individual subject, the third-level unit is the health system or clinic within the health system (cluster), and the fourth-level unit is the state. We set year 2014 as time origin for Utah when considering the policy impact of the ACA. Let  $Y_{ijkt}$  denote the binary response of having controlled diabetes at year  $t$  since policy changes for the  $k^{\text{th}}$  subject within the  $j^{\text{th}}$  cluster of the  $i^{\text{th}}$  state,  $t = -5, -4, \dots, 0, 1, \dots, 5$ ,  $i = 1, 2, 3$ ;  $j = 1, 2, \dots, c_i$ , and  $k = 1, 2, \dots, n_{ij}$ , where  $c_i$  is the number of clusters within the  $i^{\text{th}}$  state and  $n_{ij}$  is the sample size within the  $j^{\text{th}}$  cluster of the  $i^{\text{th}}$  state. An individual subject may not be in the system for all 11 timepoints of measurement, so  $t$  will have a smaller range of values for that individual subject. Also due to the different timeline of policy changes, the number of years before and after policy changes may vary. The probability of having controlled diabetes,  $\mu_{ijkt} = E(Y_{ijkt}) = \Pr[Y_{ijkt} = 1]$ , can be described by the following segmented logistic regression model

$$\begin{aligned} \text{logit } \mu_{ijkt} &= \log \{\Pr[Y_{ijkt} = 1] / \Pr[Y_{ijkt} = 0]\} \\ &= \beta_{0ijk} + (t + 5) \beta_{1ijk} && \text{if } -5 \leq t \leq 0, \text{ pre-period before policy changes} \\ &= \beta_{0ijk} + 5 \beta_{1ijk} + t \beta_{2ijk} && \text{if } 0 \leq t \leq 5, \text{ post-period after policy changes} \end{aligned}$$

where  $\beta_{mijk}$  ( $m = 0, 1, 2$ ) are subject-specific regression parameters, with  $\beta_{0ijk}$  being the log odds of having controlled diabetes at  $t = -5$ , and  $\beta_{1ijk}$  and  $\beta_{2ijk}$  being the slopes (annual change in log odds) for the pre- and post-periods, respectively. In the framework of a mixed-effects model, each  $\beta_{mijk}$  is modeled by

$$\beta_{mijk} = \mathbf{x}_{mijk}^T \boldsymbol{\beta}_m + \mathbf{z}_{ij}^T \boldsymbol{\gamma}_{1ij} + \boldsymbol{\gamma}_{2mijk}$$

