where  $\mathbf{x}_{mijk}$  is the vector of regressors for the fixed effects,  $\boldsymbol{\beta}_m$  is the corresponding vector of fixed-effects parameter coefficients,  $\mathbf{z}_{ij}$  is a vector of cluster-level regressors for the random effects for the  $j^{\text{th}}$  cluster of the  $i^{\text{th}}$  state,  $\boldsymbol{\gamma}_{1ij}$  is the cluster-level random-effect coefficients and is common to all  $m$ , and  $\boldsymbol{\gamma}_{2mijk}$  is the subject-level random-effect coefficients associated with the parameter  $\beta_m$  for the  $k^{\text{th}}$  subject within the  $j^{\text{th}}$  cluster. The random effects are assumed to follow a multivariate normal distribution with mean zero. Because the vector  $\mathbf{x}_{mijk}$  may include subject-level, cluster-level and state-level exposure variables, the fixed effects parameter vectors  $\boldsymbol{\beta}_1$  and  $\boldsymbol{\beta}_2$  represent the effects of different exposure variables on the annual changes in the pre- and post-periods. Thus, we may perform statistical tests to examine whether there are differences in trends between the pre- and post-periods overall and for each state, and whether the patterns of changes differ between the states.

Similarly for a count outcome  $Y_{ijkt}$  (e.g., number of clinical visits), we define the expected value  $\mu_{ijkt} = E(Y_{ijkt})$  and apply a Poisson regression model based on the natural log link function. The log expected number of clinical visits,  $\log(\mu_{ijkt})$ , can be modeled with the aforementioned segmented mixed-effects model. The use of an offset term in the models yields the estimates of the rate of clinical visits rather than the mean number of visits. The fixed-effect parameters,  $\beta_1$  and  $\beta_2$ , represent the effects of exposure variables on the annual changes in log of incidence rates for the pre- and post-periods, respectively. For a continuous outcome  $Y_{ijkt}$ , we will model the mean,  $\mu_{ijkt} = E(Y_{ijkt})$ , with the mixed-effects model and the parameters  $\beta_1$  and  $\beta_2$  indicate the effects of exposure variables on the annual changes in the outcomes for the pre- and post-periods, respectively. All final statistical models will be assessed with respect to the goodness-of-fit and the appropriateness of model assumptions. Statistical software SAS 9.4 and R environment will be used to implement the proposed analyses.

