Furthermore, we will use the similar models as described above to evaluate post-policy impact of obesity screening and counseling (number of visits) on the outcomes such as weight loss, diabetes incidence, and diabetes outcomes (including hemoglobin A1c, controlled blood pressure, use of a statin medication). The outcome data collected after the universal coverage change (i.e.,  $t = 0, 1, \dots, 6$ ) will be used to estimate the trend of change. The number of screening and counseling will be used as a predictor in the mixed effects models. The effects of patient and practice characteristics will also be examined in the models. Statistical software SAS 9.4 and R environment will be used to implement the proposed analyses.

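### The stated model has no provider level, so Aim 2 standard errors for provider type and specialty are too small wherever provider types mix within a cluster

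*Combined protocol and SAP*

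**What the plan says.** Under Aim 2 in section 1.0, the investigators will examine "practice characteristics, including provider type, and their impact on receiving/providing obesity screening and counseling". Table 1 in section 7.2 gives the provider and practice exposures. They begin with "Practitioner type (advanced practice vs. MD/DO) -Practitioner specialty" and continue with practice size, type and setting. The table leaves the availability of all of these open.

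Section 8.0 lists receipt of counseling among the yearly binary outcomes at individual level. The first level of the model is the yearly measurement. Above it, "the second-level unit is the individual subject, the third-level unit is the health system or clinic within the health system (cluster"), and state is the fourth level. In the equation, the only random terms are a cluster vector, which "is the cluster-level random-effect coefficients and is common to all" values of m, and a subject term. The fixed-effect regressors "may include subject-level, cluster-level and state-level exposure variables"; the provider is not among the levels named. For the post-policy analyses, section 8.0 says models similar to these will be used and that "The effects of patient and practice characteristics will also be examined in the models". Nowhere does the plan give a provider random effect, a cluster-robust variance, a number of providers or an ICC.

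**The concern.** Practitioner type and specialty belong to the provider. Their effect has to be judged against how much providers of the same type differ from one another. If providers within a clinic differ in how often they counsel, for reasons other than type, patients of one provider resemble each other more than the clinic effect explains. A model with no provider term leaves that variation in the patient-level part and averages it over patients, of whom there are very many, when it should be averaged over providers. Standard errors for provider effects are then too small, and chance differences between providers can look like effects of type.

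The choice of cluster adds to this. The plan allows level 3 to be the health system. In that case practice size, type and setting also have no random effect at their own level.

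Aim 2 intends these results to identify best practices and to guide how engagement is increased. The power statement in section 8.0 offers no protection. It covers individual-level exposures only, and a large number of patients does not increase the number of providers.

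**Working it through.** The plan states no standard error, power figure or ICC for provider effects, so there is no figure of its own to reproduce.

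**Inputs**
- From section 7.2: 328,455 patients with diabetes and 2,062,499 at risk. The site counts add up to these totals.
- Assumed, because the documents are silent: m = 10 to 1,000 patients per provider, and ρ = 0.01 to 0.10 for the provider ICC of counseling receipt that remains within the cluster.

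**Step 1: understatement of the standard error.** For a covariate that is constant within provider, with equal panels, true SE / model SE = √[1 + (m − 1)ρ].

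| ρ | m = 10 | 50 | 100 | 500 | 1,000 |
|---|---|---|---|---|---|
| 0.01 | 1.04 | 1.22 | 1.41 | 2.45 | 3.32 |
| 0.05 | 1.20 | 1.86 | 2.44 | 5.09 | 7.14 |
| 0.10 | 1.38 | 2.43 | 3.30 | 7.13 | 10.04 |

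For example, √(1 + 49 × 0.05) = √3.45 = 1.86. A ratio of 3 needs m = 1 + 8/ρ, that is 801, 161 or 81 patients per provider at ρ = 0.01, 0.05 or 0.10.

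**Step 2: does the clinic random intercept absorb this?** With K providers per clinic, type varying within clinic and the clinic intercept fitted, the ratio is √{[mρ + 1 − ρ] / [(1 − ρ) + ρ(K − 1)m/(Km − 1)]}. For K = 5, m = 50 and ρ = 0.05 this is √[3.45 / (0.95 + 0.05 × 200/249)] = √(3.45/0.990) = 1.87. The clinic intercept makes almost no difference.

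**Step 3: effect on the test.** At nominal 5% two-sided, the type I error is 2[1 − Φ(1.96/r)] for ratio r: 0.10 at r = 1.2, 0.19 at 1.5, 0.33 at 2, 0.51 at 3 and 0.70 at 5.

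**Step 4: simulation.** A linear mixed model with a cluster random intercept only was fitted to 150 replicates per scenario, with m = 50.

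| Scenario | Provider ICC | SE ratio | Type I error |
|---|---|---|---|
| 40 clinics × 6 providers, type mixed within clinic | 0.05 | 1.82 | 0.29 |
| Same | 0.01 | 1.25 | 0.13 |
| 6 health systems × 40 providers, type mixed | 0.05 | 1.77 | 0.28 |
| 40 clinics × 6 providers, type constant within clinic | 0.05 | 1.01 | 0.05 |

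With 150 replicates, a rate of 0.29 has a Monte Carlo standard error of √(0.29 × 0.71/150) = 0.04.

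**Step 5: link to the cohort sizes.** Suppose all counted patients were spread over 2,000 to 20,000 providers (assumed). Panels would then be about 164 down to 16 in the diabetes cohort and 1,031 down to 103 in the at-risk cohort. With ρ = 0.01 to 0.10, the ratio runs from 1.07 to 4.16 and from 1.42 to 10.2.

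These steps assume balanced panels, a linear scale and one response per patient. The planned model is logistic with repeated years, so the figures show order of size only.

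**The case against.** **The cluster effect already links these patients.** A reader might infer that patients of one provider are treated as wholly independent. They are not: they share the clinic or health-system random effect, and only the extra within-cluster correlation is missed. If every provider in a clinic is of one type and clinic is the fitted cluster, nothing is lost. This part of the objection stands. It does not cover clinics with mixed types, or a model clustered on health system.

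**The size is unknown.** A reader might also infer that the standard errors are several times too small. The documents cannot support that, since they give no ICC, number of providers or panel size. Panels of 200 to 1,000 in the diabetes cohort would imply about 1,642 down to 328 providers (328,455/200 and 328,455/1,000), and nothing in the plan indicates such numbers. The counts in section 7.2 also precede the restriction to patients with two primary care visits or claims data, so analysed panels may be smaller. This stands.

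**The model is not final.** The equation is worked for controlled diabetes, other analyses use similar models, section 7.2 leaves determination of the models until after the first extraction, and section 8.0 promises checks of assumptions. All true, but none of this supplies a provider level, and the levels are stated for the modeling in general.

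**Investigators will judge clinical significance.** That filters out trivially small effects. It does not filter a sizeable chance difference between providers that carries a falsely small p-value.

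**Provider type is a secondary part of Aim 2.** This stands and limits the importance of the point. Section 1.0 also describes counseling as something patients and providers both engage in, so the provider ICC need not be large.

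**Conclusion.** The omission is certain. Provider type and specialty are to be tested in a model that has no provider-level variation to test them against. Wherever provider types mix within the fitted cluster, and providers differ at all beyond type, the standard errors for provider effects are too small.

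The size is not certain. Over the assumed range (ICC 0.01 to 0.10, 10 to 1,000 patients per provider) the ratio runs from about 1.04, which is harmless, to about 10, which would make the test meaningless. A several-fold understatement is possible with large panels but is not shown. With type constant within the fitted clinic, the ratio is about 1.0. If level 3 is the health system, the same fault extends to practice size, type and setting.

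The point is confined to provider and practice effects. Nothing here shows bias in the policy-trend analyses or in the comparison of counseled with non-counseled patients. The plan should be changed before the provider analyses are run, but the main comparisons do not depend on it.

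**What to change.** For every analysis that estimates effects of provider or practice characteristics, add the following to section 8.0:

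1. Fix level 3 as clinic and remove the choice between clinic and health system.
2. Then do one of two things. Either add a provider random intercept, in cross-classified or multiple-membership form if patients change provider between years, because subjects are then no longer nested in providers. Or keep the simpler model and use cluster-robust standard errors at clinic level. The clinic is the right unit for the robust variance, since the six health systems named in section 1.0 are too few.
3. State the rule that attributes a patient to a provider, and restrict provider-effect analyses to patients with an attributable provider. Patients who qualify only through claims may have none.
4. Report the number of providers, the number of clinics and the estimated provider ICC (where the provider intercept is fitted) beside each provider effect.

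The cost is wider intervals for provider effects, more computation (heavy for a logistic model with crossed random effects on cohorts of this size), and provider results that do not extend to patients without an attributed provider. The random-intercept option also needs a coded provider identifier, and Table 1 leaves the availability of provider data open. The clinic-robust option needs only a clinic identifier and is the practical fallback.

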## 1.0 Objectives

The overarching goal of this proposal is to understand the comparative effectiveness of obesity counseling as covered by Centers for Medicare and Medicaid Services (CMS) in improving weight loss for adults either with or at high risk of type 2 diabetes. CMS and most insurers now include obesity screening and counseling benefits, with no cost sharing to patients. Since overweight patients are at highest risk for diabetes, improved weight management services could prevent diabetes and its negative health outcomes. Beneficiaries with obesity are eligible for up to 20 face-to-face visits for weight counseling in the primary care setting. We propose comparing weight and diabetes outcomes in three states using electronic health record (HER) and claims data before and after this policy was implemented. The PaTH network brings together six academic health systems – the University of Pittsburgh/University of Pittsburgh Medical Center, Penn State College of Medicine/Hershey Medical Center, Temple University School of Medicine/Temple Health, and the Johns Hopkins University/Johns Hopkins Health System/Johns Hopkins Health Care, Geisinger Health Systems, and The University of Utah – to function as an integrated research network and learning health system, providing an infrastructure for observational studies, such as the one proposed here, that require populations beyond a single health system to answer important patient-centered health services questions ([www.pathnetwork.org](http://www.pathnetwork.org)). Using the PaTH Clinical Data Research Network (CDRN) infrastructure, we propose the following specific aims:

**Aim 1: Evaluate the impact of universal preventive service coverage for obesity screening and counseling on weight loss, diabetes incidence, and diabetes outcomes, in patients with diabetes or at high risk for diabetes (defined by body mass index (BMI)  $\geq 25$ ).** We will determine how the annual probability of receiving obesity and/or nutritional counseling (as defined by Current Procedural Terminology (CPT) code) changed pre- and post-policy across all insurers in a cohort of patients with diabetes and at high risk for diabetes. We hypothesize that individual patients are more likely to receive counseling following coverage implementation. Further, we hypothesize that patients who receive a greater number of face-to-face visits will have greater weight loss compared to those who receive fewer visits.

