The proposed work leverages the novel infrastructure of the Patient-Centered Outcomes Research Institute-funded PaTH Clinical Data Research Network (CDRN), a partnership of four Mid-Atlantic academic health systems (Penn State Hershey Medical Center, University of Pittsburgh Medical Center, Temple Health System, and Johns Hopkins Health System) that have established governance to operate as an integrated research network. In 2015, the University of Utah and Geisinger Health System also joined PaTH, creating an electronic health record (EHR)-based data infrastructure across three states (Maryland, Pennsylvania, and Utah).

[figure not shown]
We have additionally added a focus on rural/urban differences in provision of obesity screening and counseling and the resultant impact on weight loss and diabetes incidence. Rural populations have a 17% higher prevalence of diabetes when compared to their urban counterparts. As a result, diabetes is the second highest priority for Rural Healthy People 2020. Additionally, rural populations have lower rates of guideline-concordant diabetes services, although this has been inadequately investigated. Studies report adults with diabetes living in rural communities are less likely to receive adequate diabetes-related care than non-rural residents, but are limited in study design (i.e., reliant on patient self-report or medical expenditure data). We propose leveraging the novel infrastructure of the Patient-Centered Outcomes Research Institute-funded PaTH CDRN to understand the rural and urban effects on diabetes and its complications. The integration of six large health institutions spanning a diversity of rural and urban populations has the unique opportunity to overcome limitations of prior studies by using health record data. In this way, our proposed study will address important gaps in our understanding of rural/urban differences in diabetes outcomes and guide future approaches to address and eliminate disparities.

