### 7.2 Study Procedures

For the specific needs of this proposal, we will define 2 patient cohorts using the PaTH Network: (1) Diabetes cohort and (2) At-risk for diabetes cohort. As demonstrated in the table below, there are over 328,000 patients with a diagnosis of diabetes (defined as age 18 and older with a diagnosis of diabetes mellitus – ICD9 250.xx) and over 2 million patients at risk for diabetes (defined as age 18 and older with a BMI of  $\geq 25$ ) within the PaTH network.

Patient Characteristics	Penn State University (N=25,219)	University of Pittsburgh (N=150,589)	Johns Hopkins University (N=60,324)	Temple University (N=40,536)	University of Utah (N=51,787)	PaTH Total (N=328,455)
Patients with Diabetes						
Insurance type						
Private	9,874 (38%)	60,223 (40%)	32,371 (54%)	5,261 (13%)	21,264 (41%)	128,993 (39%)
Medicaid	1,890 (8%)	10,165 (7%)	727 (1%)	21,759 (54%)	4,189 (8%)	38,730 (12%)
Medicare	12,998 (52%)	54,675 (36%)	22,826 (38%)	10,916 (27%)	23,997 (46%)	125,412 (38%)
Uninsured	457 (2%)	11,625 (8%)	485 (1%)	2,599 (6%)	2,337 (5%)	17,503 (5%)
Race						
White	21,780 (86%)	116,056 (77%)	32,544 (54%)	14,347 (35%)	39,580 (76%)	224,307 (68%)
African-American	1,679 (7%)	15,336 (10%)	20,053 (33%)	14,656 (36%)	944 (2%)	52,668 (16%)
Other	1,760 (7%)	19,197 (13%)	7,727 (13%)	11,533 (29%)	11,263 (22%)	51,480 (16%)
Hispanic Ethnicity	1,054 (4%)	697 (0.5%)	2,002 (3%)	7,356 (18%)	6,077 (12%)	17,186 (5%)
Female Gender	12,014 (48%)	70,623 (47%)	30,912 (51%)	22,485 (55%)	25,727 (50%)	161,761 (49%)
Patients At-Risk for Diabetes						
	(N=167,799)	(N=950,020)	(N=471,860)	(N=212,314)	(N=260,506)	(N=2,062,499)
BMI						
25-29.9	69,353 (30%)	433,799 (31%)	226,113 (32%)	92,807 (31%)	122,583 (31%)	944,655 (32%)
30-34.9	48,353 (21%)	268,236 (19%)	128,799 (18%)	60,330 (20%)	87,023 (22%)	592,741 (20%)
35-39.9	25,388 (11%)	128,113 (9%)	58,072 (8%)	29,930 (10%)	70,774 (18%)	312,277 (10%)
40+	24,705 (11%)	94,550 (7%)	43,377 (6%)	23,321 (8%)	25,410 (7%)	211,363 (7%)

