***Diabetes Cohort Definition.*** During year 1 of the proposed project, the investigative team, in collaboration with the PaTH Network, will identify a valid cohort of patients with type 2 diabetes. The cohort of patients under study will be defined as all patients age 18 and older with an indication of type 2 diabetes during the proposed study time frame. Patients will be classified as having diabetes using a clinically validated algorithm: type 2 diabetes mellitus on the problem list, diabetes-specific medications, hemoglobin A1c (HbA1c) results > 7.0%, or one inpatient diagnosis code or two outpatient diagnosis codes for type 2 diabetes (ICD-9 codes 250.xx). The diabetes cohort will be further limited to patients who will likely be captured in the PaTH EHR records or claims data so that outcome assessments can occur. Thus, we will further limit the diabetes cohort to patients who have either: (1) had at least 2 outpatient primary care visits in one of the PaTH health systems in the past 3 years (since January 1, 2012), or (2) for whom claims data are available. The cohort will be dynamic, with new patients added into the cohort after 2015 as they meet the diabetes cohort definition prospectively. The observational period for the outcome variables will be for the 10-year period from 2009-2019, thus including 3 years of data prior to the first policy change (CMS instituting coverage for intensive behavioral therapy for obesity) and 3 years after the last policy change (Pennsylvania Medicaid expansion) under study.

Following the definition of the diabetes cohort and key diabetes outcomes and covariates as described above, an initial extraction of variables will be conducted in Year 2 of the proposed project for years 2009-2015. This early data extraction from the PaTH Network will allow for cohort validation and data cleaning and editing, as well as required programming and determination of the analysis models. We will utilize this initial data extraction in Years 2 and 3 to analyze the impact of early health policy changes, as well as to prepare a manuscript of both the protocol and early findings of policy impact. The final data extraction will occur during the final quarter of Year 4 of the proposed project, allowing for completion of a ten-year time period (2019).

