To evaluate the impact of policy changes on these outcomes, we will examine how these outcomes change over time, in response to the policy changes. As descriptive analyses, we will plot the mean trajectory of each yearly outcome at clinic level, health system level and state level. The statistical modeling of patterns of changes in individual level outcomes will be carried out through multi-level mixed-effects models. The mixed-effects model is a common and popular modeling technique for longitudinal data. A mixed-effects model can accommodate within- and between-subjects variability, as well as serial correlations. In addition, it has the flexibility to incorporate time-dependent covariates, incomplete data, and heteroscedasticity of the variances and correlations. The mixed-effects model will be specified in a multi-level fashion so that different levels of variability (e.g., individual characteristics, social environment, built environment) can be taken into account. The pattern of changes in the outcome will be assessed for pre- and post-periods, respectively, based on the piecewise/segmented regression models. The slope of each segment indicates the trend of change in diabetes outcome in that period. Therefore, the change in the trend/slope post-policy implementation may reveal the actual impact of the new policy controlling for baseline level and trend. Such modeling strategies share the same spirit of interrupted time series analysis. While the classical interrupted time series design often generates a single long series of data, we have a large number of short series from each individual subject, namely, longitudinal data. Depending on the types of the outcomes, we will specify mixed-effects models based on logistic

regression for a binary outcome, Poisson regression for a count outcome and linear regression for a continuous outcome as detailed below.

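### The cluster random effect cancels exactly from the pre/post change in slope, so the individual-level policy test carries no allowance for clusters that respond differently to the policy

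*Combined protocol and SAP*

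**What the plan says.** Section 8.0 models yearly outcomes with a segmented mixed-effects regression: for each subject an intercept at t = -5, a pre-policy slope and a post-policy slope (m = 0, 1, 2). Each parameter is a fixed part, plus a cluster part z_ij'gamma_1ij, plus a subject part gamma_2mijk. The subject part is indexed by m. The cluster part is not, and the text confirms that gamma_1ij "is the cluster-level random-effect coefficients and is common to all" m. The cluster may be the health system or a clinic within it; the plan leaves this open.

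The policy is judged by the difference between the slopes: "the change in the trend/slope post-policy implementation may reveal the actual impact of the new policy controlling for baseline level and trend". Tests of it are foreseen overall and by state.

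The test bears on the first hypothesis of Aim 1 in section 1.0 ("We will determine how the annual probability of receiving obesity and/or nutritional counseling" changed around the policy). Section 8.0 lists counselling among the yearly binary outcomes ("receiving annual eye exam, receiving obesity and/or nutritional counseling").

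Three planned steps could touch the issue. Section 7.2 uses the first extract for "required programming and determination of the analysis models". Section 8.0 says "we will plot the mean trajectory of each yearly outcome at clinic level, health system level and state level". It also promises a general check of fit and assumptions. None names a test of cluster variation in slope change, or says what would follow from finding it.

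**The concern.** A multi-level model is used here so that the uncertainty of a policy effect reflects the units through which the policy acts. Clinics and systems can take up a coverage change at different speeds. Such variation averages out over the number of clusters, not the number of patients. If the tested contrast contains no cluster variance, the standard error shrinks with patient numbers alone, which are very large here.

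The subject-level random slopes do not repair this. They can absorb the extra variance, but they divide it by the number of patients. Cluster-level covariates in the fixed part cover only differences that are measured and included, and the plan says only that they may be included.

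At stake are the p-values and intervals of the individual-level segmented pre/post analysis: the Aim 1 change in counselling and the pre/post diabetes outcomes. The post-policy-only models for number of visits (Aim 2) and the rural/urban trend models do not use this contrast and are outside the point.

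**Working it through.** The plan derives no standard error or power for this test, so there is no figure of its own to reproduce.

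**Step 1: algebra (no assumptions).** Let u = z_ij'gamma_1ij. At year t the intercept loads 1, the pre-slope min(t,0)+5 and the post-slope max(t,0).
- Cluster contribution: u[1 + min(t,0) + 5 + max(t,0)] = (t+6)u. The multipliers run 1, 2, ..., 11 for t = -5, ..., 5.
- The cluster SD is therefore forced to grow 11-fold over the period. A cluster 0.3 log odds above average at t = -5 must be 3.3 above at t = 5.
- Slope change: (beta_2 + u) - (beta_1 + u) = beta_2 - beta_1. The cluster term vanishes whatever its variance, for the logit, log and identity links alike.

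**Step 2: illustrative size.** From the section 7.2 table: 25,219 + 150,589 + 60,324 + 40,536 + 51,787 = 328,455 patients with diabetes. The largest system ("University of Pittsburgh (N=150,589") holds 150,589/328,455 = 46%. These counts cover five of the six systems and precede the visit/claims restriction.

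Assumed, because the documents are silent: outcome prevalence 70%; contiguous 5-year windows per patient; subject SDs of 1-2 (intercept) and 0.1-0.5 (each slope); two-sided 5% test with cutoff 1.96; between-cluster SD of slope change tau.

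For a window with design X, linearised V = I/(p(1-p)) + X D X' with D = diag(s0², s1², s1²). Information X'V⁻¹X is averaged over the seven windows and multiplied by N. The model SE of beta_2 - beta_1 runs from 0.0026 (s0 = 1, s1 = 0.1) to 0.0032 (s0 = 2, s1 = 0.5).

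True SE² = model SE² + tau²/J. Type I error = 2[1 - Phi(1.96 × model SE / true SE)]. For J = 50, tau = 0.02, model SE 0.00261: true SE = sqrt(0.00261² + 0.0004/50) = 0.00385, ratio 0.678, type I error 18%.

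For the five unequal systems, effective J = 328,455² / (sum of squared sizes) = 3.45.

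| Clusters | tau = 0 | tau = 0.01 | tau = 0.02 |
|---|---|---|---|
| 50 equal clinics | 5% | 7-9% | 14-18% |
| 200 equal clinics | 5% | about 6% | 7-9% |
| 500 equal clinics | 5% | about 5% | about 6% |
| Five equal systems* | 5% | 25-32% | 51-58% |
| Five systems, table sizes* | 5% | 32-39% | 58-64% |

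*Only if the systems are regarded as a sample from a wider population of systems.

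If the visit/claims restriction halves N, the tau = 0.02 figures become 10-12% (50 clinics) and 6-7% (200). At tau = 0.02, intervals allowing for tau and using t on J-1 df are 1.4-1.5 times as wide with 50 clinics and 1.1 times with 200.

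For Aim 1 counselling in the at-risk cohort (N = 2,062,499), with tau = 0.02 and an assumed annual counselling rate of 2%, 5% or 10%, type I error is 13-14%, 22-24% or 30-35% with 50 clinics, and 7%, 10% or 13-15% with 200.

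**Step 3: simulation.** The continuous-outcome version of the documented model was fitted to simulated data, 400 runs per setting, with assumed intracluster correlations (ICC) of the slope change. At ICC 0 the rejection rate was 0.028 (50 clusters of 200) and 0.060 (5 clusters of 400). At ICC 0.01 it was 0.24 and 0.35. A cluster effect specific to each m, tested on J-1 df, gave 0.02-0.06 throughout. This confirms direction and mechanism. The ICCs are not calibrated to the SDs above.

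**The case against.** The strongest objection concerns the target of inference. Section 8.0 says the models yield an average change at individual level, and the study is of one named network. If inference is to the participating systems, differences between their responses are not sampling error, and the five-system figures do not apply. This stands. A reader might infer from them that the planned test has a false-positive rate above one half. The documents do not support that: they fix neither the cluster level, nor the target population, nor the SD.

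Second, the inflation shrinks as clinics multiply. Sections 2.1 and 2.2 describe many outpatient practices and coverage of nearly all Pennsylvania counties, so clinic counts well above 50 are plausible. This also stands: at 500 equal clinics the rate is about 6%.

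Third, the plan has partial safeguards: cluster- and state-level covariates with separate coefficients for each slope, trajectory plots, model determination on the first extract, and a goodness-of-fit check. They could reveal the problem, but none specifies a test or a remedy. The optional clinic-level aggregate analysis reuses the same framework.

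Fourth, the power paragraph has investigators judge clinical relevance, and the spurious effects are small. With SD 0.02 and the five systems at table sizes, 95% lie within 0.022 log odds per year (odds ratio about 1.02). That limits over-interpretation of point estimates but does not correct an interval that is too narrow.

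**Conclusion.** The point holds in conditional form and should be fixed. Two consequences are certain from the equation as written: the 11-fold growth in cluster SD, and the exact cancellation of the cluster effect from the policy contrast. It follows that unexplained cluster differences in slope change have no term in the individual-level segmented test. If such differences exist and clusters are random, standard errors are too small and type I error exceeds its nominal level. If they do not exist, the test is sound.

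The size cannot be settled from the documents. Depending on the assumed SD and clinic count, it ranges from negligible (several hundred clinics) to material (50 or fewer).

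A reader might also infer that the plan ignores clustering altogether. It does not: it has a cluster random effect and allows cluster covariates, but the random effect is specified so that it cannot reach the contrast being tested.

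**What to change.** 1. Replace gamma_1ij by gamma_1mij: at minimum separate cluster random effects on the intercept and on the slope change, with an estimated covariance. Name the clinic as the cluster.
2. Name cluster-robust standard errors with a small-sample correction as the fallback, since the clinic covariance together with subject effects may not converge in a logistic model of this size.
3. State the target of inference.
   - If it is the participating systems, interact system indicators with both slopes and state the weights of the overall contrast. This does not widen the system-level standard error; only the clinic effect does. State indicators should not be added as well: systems nest within states, so six system and three state columns have rank 6. State contrasts can be formed from the system slopes.
   - If it is health systems in general, say that five or six systems support only small-sample t inference. An unweighted mean of system slope changes is then available, but it targets the average system and not the individual-level average that section 8.0 describes.
4. Add to the planned model checks a test of the between-cluster variance of slope change, and report its estimated SD.

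The cost is a revised random-effects line, one named check and a sentence on the target of inference, plus heavier computation and wider intervals. With several hundred clinics the widening should be slight.
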